## PAREXEL International Statistical Analysis Plan

(iii) Subtract the residual activity from the observed FVIII:C at each time point

(iv) Estimate the elimination half-life from the "corrected" FVIII:C vs time data

All individual FVIII:C versus time data sets will be analysed by non-compartmental analysis (NCA) using Phoenix WinNonlin v. 6.3.

### **6.1.5.3 ITI Outcome**

Patients may achieve 1 of 4 ITI outcomes:

1. ITI success
2. Partial success
3. Treatment failure
4. Not determinable due to withdrawal during the ITI period.

The ITI outcome will be derived for every patient.

#### **ITI Success**

The following criteria (1, 2 and 3) have to be fulfilled at the same time within 60 weeks for a patient to be considered having achieved ITI success:

1. Negative inhibitor titer (< 0.6 BU/mL) at two consecutive visits
2. Calculated IR > 66% of the expected IR at two consecutive visits
3. Terminal Half-life ( $t_{1/2}$ )  $\geq$  7 hours

Whether ITI success has been achieved and the date on which each of the three criterions has been met will be recorded.

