### ITI period

All patients will receive rFVIIIFc 200 IU/kg daily until successful tolerization or failure or for a maximum period of 60 weeks. Inhibitor titers and FVIII activity (FVIII:C) will be assessed locally at each visit. If FVIII:C levels raise above 200 IU/dL during the ITI period, the dose should be adjusted according to investigator judgment to maintain the peak FVIII:C levels between 100-200 IU/dL.

If, after the initial 3 months, a downward trend of at least 20% in the inhibitor titer in a 6-month period is not seen, the patients should be regarded as a treatment failure and complete the end of treatment visit as soon as possible.

Patients may achieve 1 of 4 outcomes: ITI success, partial success, treatment failure or not determinable due to withdrawal during the ITI period.

ITI success is defined as achieving all 3 of the following criteria in the following order 1, 2 and 3:

1. Negative titer for inhibitor (<0.6 BU/mL by the Nijmegen-modified Bethesda assay) in 2 consecutive determinations
2. Incremental recovery (IR) > 66% of the expected IR, in 2 consecutive determinations.
3. Elimination half-life ( $t_{1/2}$ )  $\geq$  7 hours

A patient who achieves ITI success within 60 weeks continues into the tapering period. A patients who achieves partial ITI success or failure will not continue into the tapering period but conduct the end of study visit.

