### 7.1.2 ITI period

The first dose of rFVIIIFc will be administered at the baseline visit and the ITI treatment will continue until ITI success or failure is declared, or for a maximum of 60 weeks. The ITI regimen

consists of daily administration of rFVIIIFc (200 IU/kg per day), which may be given as once daily injection or divided in two injections per day at the discretion of the investigator.

Visits will occur 2 and 4 weeks after the baseline visit and then every 4th week. For patients who achieves an IR >66% of the expected IR for each specific patient as per investigator judgment, the visit frequency will be changed to every other week.

During the ITI period patients will undergo procedures and assessments as per the schedule of events (Table 1). Samples for inhibitor testing and assessment of FVIII:C levels will be analyzed at the local laboratory as well as centrally. The results from the local laboratory will constitute the primary data of the study to be used for statistical analysis.

At each visit the inhibitor titer will be assessed. If, after the initial 3 months, a downward trend of at least 20% in the inhibitor titer in any 6-month period is not seen, the patients should be regarded as a treatment failure and complete the end of treatment visit as soon as possible.

The assessment of ITI outcome is illustrated in Figure 2. Once a patient has demonstrated negative inhibitor (<0.6 BU/mL) at two consecutive visits, evaluation of IR will be performed at the next visit. When an IR >66% of the expected IR has been obtained at 2 consecutive visits, pharmacokinetic assessments to determine half-life will be performed at the subsequent visits until a half-life of  $\geq 7$  hours is attained. Patients are required to have at least a 24-hour washout prior to the half-life assessment.

An unscheduled visit after the 60-week period may be scheduled to allow the patient to get a confirmatory test, as long as the first test occurred during the 60-week period. If the second test confirms the results of the first test, the date of ITI outcome is the date of the first value, which occurred during the 60-week period. Fluctuations in inhibitor levels is common and variability in inhibitor titer is expected. Patients will be evaluated on a case-by-case basis.

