#### ITI success

The following criteria (in order 1, 2 and 3) have to be fulfilled within 60 weeks for a patient to be considered having achieved ITI success:

1. Negative inhibitor titer ( $< 0.6 \text{ BU/mL}$ ) at two consecutive visits
2. Calculated IR  $> 66\%$  of the expected IR at two consecutive visits
3. Elimination half-life ( $t_{1/2z}$ )  $\geq 7 \text{ hours}$

Whether ITI success has been achieved and the date on which each of the three criteria has been met will be recorded.

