#### 7.5.5.2.1.3 Half-life

Blood samples will be collected for analysis of FVIII:C for assessment of half-life starting at the visit after confirmed IR >66% of the expected IR. The assessment will be repeated at each consecutive visit until the elimination half-life is  $\geq$  7 hours and also at the end of treatment visit.

Samples will be drawn within 30 minutes prior and 30 ( $\pm 5$ ) minutes, 24 hours ( $\pm 60$  minutes), 30 hours ( $\pm 60$  minutes), and 48 hours ( $\pm 60$  minutes) after the rFVIIIFc injection. The dose used will be the same as the prescribed dose at the time of the visit. Patients are required to have at least a 24-hour washout prior to the half-life predose sample collection and should not have any additional doses of rFVIIIFc during the PK sampling period. If emergency dosing is required during the assessment of half-life, please contact the medical monitor for instructions for how/when to repeat the assessment.

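### The SAP requires the three ITI success criteria to hold together without naming the visits, while the protocol requires them in order, so the two texts can classify the same patient differently

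*SAP*

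**What the plan says.** **Protocol.** The synopsis states: "ITI success is defined as achieving all 3 of the following criteria in the following order 1, 2 and 3". Section 7.1.2 repeats this: "The following criteria (in order 1, 2 and 3) have to be fulfilled within 60 weeks for a patient to be considered" a success. Neither place asks that an earlier criterion still hold when a later one is met. Sections 7.5.5.1.1, 7.5.5.2.3.1 and 7.5.5.2.3.2 describe each criterion as fulfilled once its own test result has been obtained. The endpoint statements (synopsis and 6.1.1) mention neither order nor simultaneity.

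**Sequence of tests (Protocol 7.1.2).** After two consecutive negative titers, "evaluation of IR will be performed at the next visit". Once IR exceeds 66% of expected, "the visit frequency will be changed to every other week". After two such IR values, "pharmacokinetic assessments to determine half-life will be performed at the subsequent visits until a half-life of" at least 7 hours is reached. Section 7.5.5.2.1.3 has the same stopping point: "The assessment will be repeated at each consecutive visit until the elimination half-life is" 7 hours or more, with one further assessment at the end of treatment visit. Section 7.1.2 also says that titers commonly fluctuate, and adds: "Patients will be evaluated on a case-by-case basis".

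**SAP.** Section 6.1.5.3 drops the order and says that the three criteria "have to be fulfilled at the same time within 60 weeks for a patient to be considered having achieved ITI success". Patients who meet all three, but not together, count as partial success, and partial success is open only to those who complete 60 weeks of ITI. The same section derives one of four outcomes for every patient.

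**The concern.** The criteria cannot first be met together, because each test is triggered by the one before it. Criteria 1 and 2 each span two visits and criterion 3 is a single assessment, so simultaneity has no meaning until someone says which visits are compared. The SAP does not say.

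At stake is the rule for the primary endpoint. A patient who meets the criteria in order, but has a positive titer or a low IR before or at the half-life visit, can be a success in one document and not in the other. The same choice decides whether that patient is an event or is censored in the time-to-success analysis (SAP 6.3.13.1), and whether he is in the denominator for relapse (SAP 6.3.13.2). The SAP's own provision for patients who meet all three criteria separately shows that its authors foresaw this.

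A secondary matter is that the four outcome categories may not cover a patient who started tapering before week 60 but does not meet the SAP's definition of success.

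**Working it through.** The plan has no figure of its own to reproduce: no formal sample size calculation was made, and the SAP presents no confidence intervals. The check covers timing, then classification, then size.

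**1. Inputs**
- 20 treated patients (Protocol 7.1; SAP 2).
- Outcome visits every 4 weeks (±1 week) until IR first exceeds 66% of expected, then every 2 weeks (±3 days) (Protocol 7.5.1.3.4 and Table 1).
- Titers drawn at every visit (Protocol 7.5.5.1.1).
- IR measured again at the half-life visit, from the same samples (Protocol 7.5.1.3.4).

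**2. Timing.** Let t be the week of the first negative titer. The shortest nominal path is:
- t + 4: second negative titer, criterion 1 met
- t + 8: first IR above 66%
- t + 10: second IR above 66%, criterion 2 met
- t + 12: half-life test

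Gap from criterion 1 to the half-life test: 4 + 2 + 2 = 8 weeks = 56 days. If each interval uses its full window, this becomes 56 − (7 + 3 + 3) = 43 days to 56 + (7 + 3 + 3) = 69 days. Three further titers are drawn after criterion 1 is met: at the two IR visits and at the half-life visit. The test falls before week 60 when t + 12 < 60, that is, when t < 48.

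**3. Classification.** Take a patient who meets criteria 1 and 2 in order and then has a half-life of at least 7 hours, with one lapse. Two plausible readings of the SAP are shown.

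| Lapse | Protocol, literal text | SAP, judged at half-life visit | SAP, judged at last two visits |
|---|---|---|---|
| Titer ≥0.6 BU/mL at half-life visit | success | not success | not success |
| IR ≤66% of expected at half-life visit | success | not success | not success |
| Titer ≥0.6 BU/mL at second IR visit only | success | success | not success |

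The first two rows show the two documents disagreeing on either reading. The third shows the SAP disagreeing with itself, depending on which visits count.

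**4. SAP category for a patient in rows 1 or 2**
- *Still in ITI at week 60:* partial success.
- *Entered tapering earlier, for example at week 40:*
  - success is denied by the simultaneity rule;
  - partial success and failure criteria 2 and 3 all need 60 weeks;
  - failure criterion 1 does not apply if the titer fell by at least 20%;
  - not determinable needs withdrawal, which has not happened.

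  No category is left.

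**5. Size.** One patient = 1/20 = 5 percentage points. The number of patients meeting the criteria in sequence is not known in advance, so 2, 5 and 10 are assumed:

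| Sequential successes (assumed) | Primary proportion | After one reclassification | Relapse denominator |
|---|---|---|---|
| 2 | 10% | 5% | 2 to 1 |
| 5 | 25% | 20% | 5 to 4 |
| 10 | 50% | 45% | 10 to 9 |

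**The case against.** **The protocol's handling of a lapse is not established.** Figure 2 is the protocol's own flow diagram for this decision and its content is not available here. Section 7.1.2 also allows individual evaluation. A reader might infer that the protocol definitely counts a lapsed patient as a success; the documents support that only as the literal reading of the text. This objection stands and limits confidence. It does not remove the conflict in wording, and individual evaluation is not a derivation rule.

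**The missing category is a corner case.** A site would have to start tapering before week 60 despite a lapse that defeats the SAP rule, and nothing suggests how often that would happen. This stands, which is why the point is secondary. A literal reading of failure criterion 1 might also catch a very early responder whose titer had already bottomed out by month 3, but that does not close the gap in general.

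**The reporting would reveal the patient.** SAP 6.3.1 shows missing values as a separate category, SAP 6.3.12.1 tabulates each criterion and lists the day it was met, and analysis sets are settled at the data review meeting. All true, but none of this says which value is the primary result.

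**Patients who stay in ITI are covered.** A reader might infer that anyone with a lapse is unclassifiable. The SAP does not support that: after 60 weeks they are partial successes. What remains open is whether a half-life of at least 7 hours obtained before a lapse still counts once the titer is negative again. Scheduled half-life testing has stopped by then and resumes only at the end of treatment visit, although Protocol 7.1.6 permits an unscheduled test.

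**Conclusion.** The point holds as a conflict in the definition of the primary endpoint and should be fixed; confidence is moderate. The SAP adds a simultaneity requirement that the protocol text lacks and leaves its visits undefined.

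The size is 5 percentage points of the primary proportion per affected patient, with a change in that patient's Kaplan-Meier status and in the relapse denominator. This assumes 20 treated patients and the literal reading of the protocol. The 8-week gap assumes nominal visit spacing and no repeated IR or half-life tests; repeats would lengthen it.

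The documents do not support a claim that the primary result will be materially wrong, because they give no rate of lapses. Nor is this a data gap: titer and IR are both measured at the half-life visit, so a clear rule could be applied to data already being collected.

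The TPFAS definition is affected only if a patient enters tapering without meeting the SAP's success rule. SAP 6.2.2 would then leave him out, whereas Protocol 9.2 includes everyone entering tapering and SAP 6.2 plans no exclusions among patients who reach a period.

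**What to change.** - Reconcile SAP 6.1.5.3 with the protocol synopsis, Protocol 7.1.2 and Figure 2 to one success definition for the primary analysis.
- If simultaneity is kept, name the visits at which it is judged and say whether one or two consecutive values are needed. Titer and IR are both available at the half-life visit. Also say whether a half-life of at least 7 hours obtained before a lapse still counts.
- Report the other version as a sensitivity analysis.
- In SAP 6.1.5.3, assign a category to patients who meet all three criteria in sequence but not together and leave the ITI period before week 60, so that the categories cover all treated patients.
- Define TPFAS as all patients entering tapering, as in Protocol 9.2 and consistent with SAP 6.2.

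These changes concern how outcomes are classified in the analysis. No proposal is made on the clinical rule for starting tapering.

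The cost is SAP wording, one derived variable and one additional analysis, plus a check against Figure 2. No new data are needed. This is best done before database lock; after lock, the SAP's introduction provides for an addendum.

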#### **Partial Success**

Partial success is defined as fulfilling the first criteria and either the second or the third. The criteria do not need to be fulfilled at the same time. Patients who fulfil all three success criteria but not at the same time, are also counted for partial success. Partial success will only be determined for patients who have

**PAREXEL International**  
**Statistical Analysis Plan**

completed the maximum period of 60 weeks of ITI but do not fulfil the criteria for ITI success or treatment failure.

**Treatment Failure**

Treatment failure is defined as fulfilling one of the following three criteria:

1. No downward trend of at least 20% in the inhibitor titers in the six (6) months after the initial three (3) months of ITI treatment
2. Presence of a sustained positive inhibitor ( $\geq 0.6$  BU/mL) after 60 weeks of ITI
3. Negative inhibitor titer without either achieving  $IR > 66\%$  of expected IR or Terminal half-life  $t_{1/2z} \geq 7$  hours after 60 weeks of ITI

For each patient who fulfils at least one of the three criteria, the one with the lowest criterion number will be considered to be the primary reason for failure.

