#### Partial success

Partial success is defined as achieving negative inhibitor titer and one of the pharmacokinetic parameters of ITI success: IR  $> 66\%$  OR elimination half-life  $\geq 7 \text{ hours}$ .

The determination of partial success will be made only among patients who have completed the maximum period of 60 weeks of ITI but do not fulfill the criteria for ITI success or treatment failure.

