#### Treatment failure

Treatment failure is defined as fulfilling one of the following three criteria:

[figure not shown]
1. No downward trend of at least 20% in the inhibitor titers in any six (6) months after the initial three (3) months of ITI treatment
2. Presence of a sustained positive inhibitor ( $\geq 0.6 \text{ BU/mL}$ ) after 60 weeks of ITI
3. Negative inhibitor titer without either achieving IR  $> 66\%$  of expected IR or Elimination half-life  $t_{1/2z} \geq 7 \text{ hours}$  after 60 weeks of ITI

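### Failure criterion 1 is not limited to patients who are still inhibitor-positive, so a confirmed-negative patient with a flat titer can be derived as a failure instead of a partial success

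*SAP*

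**What the plan says.** Both documents define treatment failure as meeting one of three criteria (Protocol 7.1.2, Treatment failure; SAP 6.1.5.3, Treatment Failure). The SAP derives an outcome for every patient.

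- **Criterion 1.** SAP: "No downward trend of at least 20% in the inhibitor titers in the six (6) months after the initial three (3) months". Protocol: "No downward trend of at least 20% in the inhibitor titers in any six (6) months after the initial three (3) months". Neither version states an inhibitor status.
- **Criterion 2.** A sustained positive inhibitor at 60 weeks.
- **Criterion 3.** It begins "Negative inhibitor titer without either achieving IR" and covers a negative patient who reaches neither IR above 66% of expected nor a half-life of at least 7 hours by week 60.

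Protocol 7.1.2 also makes criterion 1 a stopping rule. If, after the first three months, "a downward trend of at least 20% in the inhibitor titer in any 6-month period is not seen", the patient counts as a failure and goes promptly to the end of treatment visit.

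Partial success needs a negative titer plus one of the two pharmacokinetic criteria. In the protocol it is open only to 60-week completers who meet those conditions "but do not fulfill the criteria for ITI success or treatment failure". The SAP likewise requires that they "do not fulfil the criteria for ITI success or treatment failure".

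For a patient who meets several failure criteria, the SAP says "the one with the lowest criterion number will be considered to be the primary reason for failure".

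**The concern.** Criteria 2 and 3 each name the inhibitor status they apply to. Criterion 1 does not. It is a test for lack of progress, but a patient who is negative by month 3 and stays negative has almost no room to fall further, so a good early response can satisfy it. The protocol itself warns: "Fluctuations in inhibitor levels is common and variability in inhibitor titer is expected".

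One criterion is enough for failure, and failure excludes partial success. Criterion 1 can therefore override the pharmacokinetic result on which a negative patient should be judged. The counts of success, partial success and failure, with failures split by primary reason, form the table for the primary objective (SAP 6.3.12.1). The figure of outcome against time in the same section would show such a patient as a failure from about week 36 to 39, not as a partial success at week 60.

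**Working it through.** **Timing.** Nine months is 9 × 4 = 36 weeks, which matches the 36 treatment weeks in the protocol's minimum duration (4 + 36 + 2 = 42 weeks, Protocol 7.1). In calendar months it is 9 × 52.18/12 = 39.1 weeks. Either way the window closes well before week 60.

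**Room to fall.** Negative means below 0.6 BU/mL. A 20% fall from any negative titer is less than 0.20 × 0.6 = 0.12 BU/mL.

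**Applying the rules.** The profiles below are assumed. Patients in the first four rows are negative from month 3 to week 60 and were kept on treatment. The trend is taken as the month 9 titer against the month 3 titer, a comparison the documents do not define.

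| Titer, month 3 to month 9 (BU/mL) | IR >66% | Half-life ≥7 h | Rules as written | Criterion 1 restricted |
|---|---|---|---|---|
| 0.4 to 0.4 (0%) | yes | no | failure, criterion 1 | partial success |
| 0.5 to 0.3 (−40%) | yes | no | partial success | partial success |
| 0.4 to 0.4 (0%) | no | no | failure; meets 1 and 3, reported as 1 | failure, criterion 3 |
| 0.4 to 0.4 (0%) | yes | yes | success definition met; criterion 1 also met | success |
| 50 to 50 (0%), still positive at week 60 | no | no | failure, criterion 1 | failure, criterion 1 |

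Rows 1 and 2 have the same clinical result at week 60. They differ only by a change within the negative range. In row 1 criterion 3 does not apply, because IR was reached, so criterion 1 alone produces the failure. A titer that is flat throughout shows no 20% decline under any reasonable definition of trend, so rows 1 and 3 do not depend on the two-point comparison. Row 5 shows that the restriction leaves a stagnating inhibitor-positive patient unchanged.

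**If the stopping rule is followed literally.** The row 1 patient leaves at about month 9 as a failure. He never completes the 60 weeks that partial success and criterion 3 require.

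**Comparison with the rest of the plan.** Protocol 7.5.1.3.4 keeps negative patients on outcome visits until recovery is reached or week 60. Criterion 3 exists to judge them on pharmacokinetics at that point. Protocol 7.1 and SAP section 2 describe the same 20% test, applied to the earlier ITI attempt, as a sign that tolerization has stalled. None of this fits failing a negative patient at month 9 because his titer is flat.

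**Size per patient.** 1/20 = 5 percentage points, added to failure and taken from partial success. A row 3 patient moves only between failure reasons.

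**The case against.** The best defence is that the intent is plain. The test is about stagnation, negative patients have their own visit schedule, and Protocol 7.1.2 allows case-by-case evaluation. A patient reaches week 60 only if the investigator judged criterion 1 not to apply, so the misclassification needs a programmer to apply literally what the site did not. SAP 6.3.12.1 ranks patients by best outcome and says a partial success is not also a failure. Protocol Figure 2, which could not be consulted here, might show the negative branch being assessed first.

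This shows intent but does not change the written derivation. The case-by-case sentence gives no rule. The best-outcome ranking is stated only for the prognostic-factor summary. SAP 6.1.5.3 does not cite Figure 2.

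What stands is the limit on impact. No tests or confidence intervals are planned. SAP 6.3.12.1 also tabulates each success criterion separately and lists the study day on which each was met, so a mislabelled patient can be found.

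A reader might also infer four stronger points that the documents do not support:

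- **A sizeable share of patients is exposed.** In the retrospective rescue series in Protocol 5.1.2, 7 of 12 became negative, at a median of 14.1 weeks with a minimum of 3. With no ties at the median, 1 to 3 of 12 were negative by week 13, which scales to 1/12 × 20 = 1.7 up to 3/12 × 20 = 5 of 20. This is a ceiling on the first condition only and assumes a similar population. Three of the 7 have neither normal recovery nor normal half-life reported, but the text does not say they were tested.
- **A difference of 0.01 BU/mL decides the outcome.** From 0.5, a fall to 0.41 (−18%) fails and a fall to 0.40 (−20%) does not. That depends on the assumed two-point comparison.
- **The test is undefined (0/0) when both titers are below quantification.** The zero convention in SAP 6.3.12.4 is stated for changes from baseline and descriptive statistics, not for the outcome derivation.
- **The move from *any* six months (protocol) to *the* six months (SAP) calls for a rolling check.** The two coincide at the first month 9 decision, and *any* can also mean that failure requires no six-month period with a decline. A rolling check would create new failures. Titers of 100, 80, 70 and 70 at weeks 12, 24, 36 and 48 fall 30% over weeks 12 to 36 but only 12.5% over weeks 24 to 48.

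**Conclusion.** The concern holds as a defect in the written outcome rule. A confirmed-negative patient with a flat titer over months 3 to 9 meets failure criterion 1. If he completes 60 weeks with recovery but a short half-life, he is derived as a failure instead of a partial success. If neither pharmacokinetic criterion is met, the reported reason is criterion 1 instead of criterion 3.

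Each patient of the first kind shifts two primary-objective proportions by 5 percentage points in opposite directions, assuming 20 treated. The documents do not allow the number of such patients to be estimated. The patient must be negative early, flat, short of full success, and have exactly one pharmacokinetic criterion met at week 60, so zero is possible.

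A reader might infer that the primary endpoint, ITI success, is distorted. The documents do not clearly support that, because the success definition in SAP 6.1.5.3 has no condition excluding patients who meet a failure criterion. A literal stop at month 9 could in principle pre-empt a later success, but Protocol 7.5.1.3.4 tells sites to continue negative patients.

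**What to change.** In SAP 6.1.5.3, with a matching clarification of the stopping rule and failure definition in Protocol 7.1.2:

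1. Apply criterion 1 only to patients without a confirmed negative titer (two consecutive visits below 0.6 BU/mL) by the end of the six-month window.
2. Classify confirmed-negative patients who complete 60 weeks as success, partial success or failure under criterion 3.
3. List separately any confirmed-negative patient who was stopped early under criterion 1.

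The lowest-number rule can then stay as it is. No rolling 24-week check should be added.

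The cost is wording only, with no new data or visits. If the database is already locked, the SAP's own addendum route can carry the change.

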**Figure 1**

**Study flow chart**

\* Only patients who achieve ITI success within 60 weeks

The duration of individual patient study participation will vary based on time to ITI success.

The maximum individual patient study duration is expected to be approximately 116 weeks, i.e., 6 weeks of screening + 60 weeks of treatment +16 weeks of tapering + 32 weeks of follow-up + an additional 2 weeks for safety follow-up.

The minimum individual patient study duration is expected to be approximately 42 weeks, i.e., 4 weeks of screening + 36 weeks of ITI treatment + an additional 2 weeks for safety follow-up.

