### **7.3.3 Withdrawal of patients from treatment or study**

A patient should be withdrawn from the study treatment and discontinue the study for any one of the following reasons:

- ITI treatment is interrupted for >2 weeks
- Emergent or elective major surgery. Minor surgery such as tooth extraction or insertion/replacement of central venous access device is not a criterion for withdrawal.
- The patient received systemic treatment with chemotherapy and/or other immunosuppressant drugs. Use of corticosteroids for the treatment of asthma or management of acute allergic episodes is allowed with the exception of systemic corticosteroid treatment given to children daily or on alternate days at  $\geq 2$  mg/kg per day of prednisone or its equivalent or  $\geq 20$  mg/day if the duration is longer than 14 days.
- The patient is receiving concomitant immunomodulation.
- The patient is receiving emicizumab.
- The patient uses FVIII products other than rFVIIIFc (exception allowed for 1 emergency or accidental use).
- The patient or his legally authorized representative withdraws consent.
- If, in the clinical judgment of the investigator, it is not in the patient's best interest to continue with the study treatment.
- The patient enrolls into another interventional clinical study in which an investigational treatment or approved therapy for investigational use is administered.
- The patient is unwilling or unable to comply with the protocol.

The reason for the patient's withdrawal from the study must be recorded in the patient's case report form (CRF).

When a patient is withdrawn, the date of last rFVIIIFc dose and the date and reason for withdrawal (see above) should be clearly described in the relevant sections of the CRF. If a patient is removed from treatment because of an adverse event (AE), the reason for treatment withdrawal should always be stated as 'adverse event' irrespective of whether this was the investigator's or the patient's decision. The patients should be followed until the event has resolved, stabilized or returned to baseline.

The withdrawn patient should be examined, whenever possible, irrespective of the reason for withdrawal, as soon as possible. Relevant samples should be obtained and all relevant assessments should be completed, preferably according to the schedule for end of treatment visit. The CRF should be completed.

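### SAP failure criterion 1 tests the 20% titer fall only in months 3 to 9, where the protocol says any six months, and can misclass a patient on either reading of the protocol

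*SAP*

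**What the plan says.** **Protocol.** Section 7.1.2 (ITI period) says that if, after the first 3 months, the required fall "in any 6-month period is not seen, the patients should be regarded as a treatment failure and complete the end of treatment visit" promptly. The treatment failure definition in the same section gives, as criterion 1, absence of a 20% fall "in the inhibitor titers in any six (6) months after the initial three (3) months of ITI treatment". The synopsis uses the indefinite article: the rule applies if "a downward trend of at least 20% in the inhibitor titer in a 6-month period is not seen". None of these texts ends the rule at month 9.

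**SAP.** Section 6.1.5.3 requires the fall to be absent "in the inhibitor titers in the six (6) months after the initial three (3) months of ITI treatment". It also states: "The ITI outcome will be derived for every patient". The other routes are limited as follows:
- Failure criteria 2 and 3 apply only after 60 weeks of ITI.
- Partial success is open only to patients who have "completed the maximum period of 60 weeks of ITI but do not fulfil the criteria for ITI success or treatment failure".
- The not-determinable outcome needs a withdrawal reason from protocol 7.3.3. That list opens with "A patient should be withdrawn from the study treatment and discontinue the study for any one of the following reasons" and contains no titer plateau; the nearest item is general investigator judgment.
- If several failure criteria are met, the lowest-numbered one is the primary reason.

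SAP 6.3.12.1 counts failures and splits them by primary reason. Its outcome listing reserves not determinable for withdrawal on other grounds before week 60. SAP 6.3.13.1 censors patients who stopped for lack of a 20% trend at the time they failed, with no month-9 limit.

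**The concern.** The SAP replaces *any* with *the* and gives no reason. The outcome table is the main output for the primary objective, so its categories should follow from the written criteria. Here the literal criteria and the protocol can disagree about a patient, and the direction depends on what *any* was meant to say. What is at stake is the split between failure, partial success and not determinable, the primary reason given for failure, and the date from which the patient enters the outcome-versus-time figure. In an open-label study, an unclear class would have to be settled ad hoc.

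**Working it through.** **Step 1: calendar.** Protocol 7.1 gives a minimum participation of 42 weeks: "4 weeks of screening + 36 weeks of ITI treatment" plus 2 weeks of safety follow-up. With 4-week months, (3 + 6) × 4 = 36 and 4 + 36 + 2 = 42, so the stated figure is reproduced. The same convention fits protocol Table 2, footnote a, which calls the maximum ITI period 15 months (60 / 4 = 15). Calendar months would give 9 × 4.348 = 39.1 weeks of ITI.

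The SAP window therefore closes at week 36, or at about week 39 with calendar months. The time from there to week 60 is 60 − 36 = 24 weeks, or 60 − 39 = 21 weeks. Five 4-weekly visits fall inside it either way: weeks 40, 44, 48, 52 and 56.

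**Step 2: if *any* means a rolling window.** Neither document defines how the trend is computed. I take fall = 1 − last titer / first titer in the window, with no assay noise. Illustrative titers (assumed) are 50, 45, 40 and 35 BU at weeks 12, 16, 20 and 24, then 35 throughout.

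| Window (weeks) | Fall |
|---|---|
| 12–36 (the SAP window) | 1 − 35/50 = 30.0% |
| 16–40 | 1 − 35/45 = 22.2% |
| 20–44 | 1 − 35/40 = 12.5% |
| 24–48 and later | 0% |

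SAP criterion 1 is not met. The protocol would regard him as a failure at week 44. With 26-week windows and linear interpolation, weeks 13–39 fall 28.2%, weeks 17–43 fall 20.0% and weeks 18–44 fall 17.6%, so the result is the same. At week 44, failure criteria 2 and 3 and partial success are closed because 60 weeks have not passed, and no specific 7.3.3 reason applies.

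**Step 3: if one falling window is enough to avoid failure.** The patient in Step 2 is then not stopped at week 44, and the gap does not arise. The mismatch runs the other way. Assume 40 BU to week 36, then a drop of 5 BU every 4 weeks, in a patient kept on under the case-by-case evaluation mentioned in protocol 7.1.2.
- Weeks 12–36: 1 − 40/40 = 0%. With calendar months, weeks 13–39: the titer at week 39 is 40 − 5 × 3/4 = 36.25, a fall of 9.4%. SAP criterion 1 is met either way.
- Weeks 20–44: 1 − 30/40 = 25%. Protocol criterion 1 is not met.

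Having met an SAP failure criterion, he is excluded from partial success. On this trajectory he is at 40 − 5 × 6 = 10 BU at week 60 and fails on criterion 2 anyway, so only his SAP primary reason changes, to criterion 1. The exclusion changes his category only if a steeper fall brings a negative titer plus adequate recovery or half-life by week 60.

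**Step 4: size.** One patient among the 20 planned is 1/20 = 5 percentage points.

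**The case against.** The strongest reply is that the rolling window appears nowhere in the documents. In ordinary grammar, no fall in any six months means that no such period exists, so a single falling period is enough. The protocol also alternates between *a* and *any* for this rule and for the matching eligibility rule, which looks like loose drafting. Applied as treatment proceeds, this reading decides almost every case when the first window closes at about week 36, matching the 36-week minimum. SAP criterion 1 is then close to a restatement of the protocol. The rolling reading also needs an exemption that neither document contains: a patient stably negative for 24 weeks while awaiting recovery or half-life results would otherwise show no 20% fall and count as a failure.

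This stands. A reader might infer that the protocol prescribes a rolling stopping rule which the SAP contradicts; the text does not establish that. A reader might also infer that a late-stopped patient has no place in the outcome table. That goes too far: SAP 6.3.13.1 gives such patients a failure time, and the wording on other withdrawals in 6.3.12.1 points away from not determinable.

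The reply does not remove the point. The literal text of criterion 1 is narrower than those two sections imply. On the one-window reading it is not equivalent to the protocol for a patient kept on past week 36. The case-by-case sentence allows that in principle, although it closes a paragraph on confirmatory tests and its scope is not stated.

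**Conclusion.** The point holds as an unexplained narrowing that leaves criterion 1 out of step with the protocol on either reading. On the rolling reading, a stop after about week 36 (39 with calendar months) and before week 60 lacks a literal failure criterion. On the one-window reading, a late faller can be failed by the SAP alone.

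The effect is confined to the split between failure, partial success and not determinable, at 5 percentage points per patient among 20. The documents give no basis for estimating how many patients are involved, and it may be none. The late-stop gap does not alter the ITI success count. The study is descriptive and outcomes are listed by patient, so an odd classification would be visible. The worked cases rest on assumed titers and on an endpoint-to-endpoint measure of the fall. This is a modest clarification to the primary-objective table, worth making because it is nearly free.

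**What to change.** 1. In SAP 6.1.5.3, criterion 1, restore the protocol's *any six (6) months*.
2. Have the sponsor confirm before database lock which reading applies. If only months 3 to 9 are intended, state this as a change from the protocol.
3. Add one sentence: a patient whose ITI is ended before week 60 for lack of a 20% titer fall is a treatment failure under criterion 1, dated at the stop. This agrees with 6.3.12.1 and 6.3.13.1 and is sound on either reading.
4. Do not write a rolling window into the SAP unless the sponsor confirms it, together with an exemption once the titer is below 0.6 BU/mL.

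The cost is a few sentences of SAP text. Titers and stop dates are already collected, so no new data or visits are needed. The downside is that the failure count may be slightly higher.
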